4.2 OTHER TREATMENTS, EMERGENCY PROCEDURES, RESTRICTIONS

This section provides information on restrictions regarding concomitant treatment prior to randomization and during the trial, including a definition on rescue therapy for the treatment of worsening of HS.

4.2.1 Other treatments and emergency procedures

Systemic steroids dosed intravenously or orally for less than 24 hours as treatment of infusion or anaphylactic reactions are permitted and do not lead to treatment discontinuation nor to assignment as treatment failures in the ITT analysis.

4.2.1.1 Systemic hypersensitivity including infusion reaction and anaphylactic reaction

In case of systemic hypersensitivity including infusion reaction and anaphylactic reaction emerging during or after infusion / injection(s) of trial medication, the investigator should consider in accordance with severity of the reaction and local standard of care to

- Immediately interrupt the infusion (if i.v) or stop further injections (if s.c.).
- Treat with systemic anti-histamines, intravenous steroids, and in case of a severe allergic reaction (e.g., anaphylactic reaction) epinephrine
- in case of s.c. administration give epinephrine in case of signs of hypersensitivity and add further treatments, e.g. oxygen, iv fluids, antihistamines and systemic corticosteroids as needed.

Also draw a plasma sample for IgE and ADA as detailed in the Lab Manual in the ISF (Central laboratory). Consider also the evaluation of histamine, serum tryptase, and complement components.

In case of infusion reaction, based on patient's clinical course and medical judgment, the infusion may be re-initiated in case of mild or moderate infusion reactions (according to RCTC grading) at lower speed with gradual increase to complete the infusion as detailed in the Instructions for Preparation and Handling of Spesolimab/Placebo in the Investigator Site File. In any case, the total duration of infusion should not exceed 180 minutes (3 hours). If the infusion exceeds 180 minutes, it should be stopped and the infusion should be skipped. Patient should be called for the next scheduled visit as planned.

In case of systemic hypersensitivity, based on patient's clinical course and medical judgment, the injection(s) may be continued in case of mild or moderate systemic hypersensitivity (according to RCTC grading) to complete the injections as detailed in the Instructions for Preparation and Handling of Spesolimab/Placebo in the Investigator Site File.

In case of anaphylactic reaction based on the criteria discussed in the statement paper from Sampson HA ([Appendix 10.13 \[R11-4890\]](#)) suspected to be caused by the trial medication, the investigator should discontinue treatment permanently with spesolimab.

When a delayed hypersensitivity reaction is suspected, please draw a blood sample for laboratory assessment and evaluate for signs of extra-cutaneous organ involvement. The decision to discontinue treatment and/or restart treatment after resolution of the reaction should be based on reaction type and severity.

4.2.1.2 Severe infections (according to RCTC grading), serious infections, opportunistic or mycobacterium tuberculosis infections

Treatment of the infection should be initiated promptly according to local standard of care. No further trial medication should be administered until the active infection has resolved. Treatment with spesolimab may be restarted when the patient has recovered according to investigator's assessment.

4.2.1.3 Malignancies

In case of occurrence of malignant neoplasm other than appropriately treated basal cell carcinoma or squamous cell carcinoma of the skin or in situ carcinoma of uterine cervix, the investigator should permanently discontinue treatment with spesolimab. Diagnostics and treatment have to be initiated according to local standard of care.

4.2.1.4 Suicidality

In case the patient develops suicidal ideation of type 4 or 5 in the C-SSRS (i.e. active suicidal thoughts with method and intent but without specific plan, or active suicidal thoughts with method, intent and plan) or any suicidal behavior (i.e. actual attempt, interrupted attempt, aborted attempt, or preparatory acts or behavior), the patient should immediately be referred to a mental health professional for further work-up and permanently discontinue trial treatment.

Overall, the choice of Standard of Care treatment will be left at the discretion of the investigator. The sponsor will not provide/supply SoC treatment (s) to the sites.

Any of the above treatments in this section must be documented in the source data, including an estimate on dispensed medication, and documented in CRF (concomitant medications) and the corresponding AE if applicable.

4.2.2 Restrictions

4.2.2.1 Restrictions regarding concomitant treatment

The following medications/ medication classes are restricted during trial treatment and prior to visit 2 for durations as specified below. Please see [section 3.3.4](#) for withdrawal information regarding the use of restricted medications.

Table 4.2.2.1:1 Restricted Medications.

Medication	Washout period prior to V2 (baseline)
Systemic antibiotics ¹	4 weeks
Systemic corticosteroids ²	1 week
Biologics causing immunosuppression	12 weeks or 5 half-lives whichever is longer
Other systemic immunomodulatory and immunosuppressive agents	4 weeks or 5 half-lives whichever is longer
Live vaccines	6 weeks
Opioid analgesics	2 weeks
Spirolactone ³	1 week
Metformin ³	1 week
Topical cannabis oil ⁴	1 week
Topical corticosteroids for HS ⁵	1 week

¹ For more information on the use of systemic antibiotics please see [section 4.2.2.3](#).

² Systemic corticosteroids as short courses can be used for indications other than HS.

³ Restricted if used for HS. If used for non-HS indication, dose should be stable for at least 12 weeks prior to V2.

⁴ Restricted if used over HS-affected areas. Other alternative therapies for HS are restricted, unless permitted after discussion with PI and trial team.

⁵ Topical corticosteroids are allowed for indications other than HS if the areas are not affected by HS concurrently.

4.2.2.2 Rescue treatment

HS Disease worsening is defined as a 150% increase in AN count from baseline. **Rescue medication** is generally defined as the treatment for disease worsening and includes systemic antibiotics and/or immunosuppressive biologics such as TNF-inhibitors. In this trial, immunosuppressive biologics are not allowed. For more information on the use of antibiotics during the trial see [section 4.2.2.3](#). The sponsor will not provide/supply these treatment(s) to the sites.

4.2.2.3 Antibiotic use during the trial

Non HS use:

Systemic antibiotics can be used for indications other than HS and for a duration of less than or equal to 4 weeks during the entire course of the trial (from randomization up to the last treatment administration).

HS disease worsening (as defined above in [section 4.2.2.2](#)):

At or after week 4, if the patient requires systemic antibiotics for disease worsening as per the investigator, monotherapy with either doxycycline 100mg orally twice daily or alternative as per investigator discretion, may be used for a maximum period of 2 weeks, and not more than a total of 4 weeks during the entire course of the trial.

Concomitant use of systemic antibiotic therapy for treatment of HS other than for disease worsening, or before week 4, is not allowed and will lead patient to permanent treatment discontinuation (see [Section 3.3.4.1](#)).

4.2.2.4 Analgesics use during the trial

Opiate analgesics are restricted for HS and non-HS indications.

If a subject is on a non-opioid analgesic for HS and non-HS indication (e.g. osteoarthritis), the subject may continue the analgesic, provided the dose is stable for 14 days prior to Baseline and is anticipated to remain stable throughout the study.

If a subject's pain (HS-related or non-HS-related) worsens after Baseline, they may initiate or increase the non-opioid analgesic therapy.

Use of analgesics will be documented in the Patients Diary and the CRF.

4.2.2.5 Lesion intervention

In the event that an acutely painful lesion occurs that requires immediate intervention, physicians will have the option to perform protocol-allowed interventions.

Only two types of interventions are allowed: Intra-lesional steroid and Incision and Drainage (I&D). If I&D is performed, only over the counter antiseptic wash can be used. Concomitant medications associated with the lesion intervention must be captured in the medical records. A total of two protocol-allowed interventions are permissible. An intervention can maximally occur on two different lesions at the same time or on the same lesion at two different study visits. If the subject requires more than two interventions, then they may be discontinued from the study.

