2. TRIAL OBJECTIVES AND ENDPOINTS

2.1 MAIN OBJECTIVES, PRIMARY AND SECONDARY ENDPOINTS

2.1.1 Main objectives

This is a proof of clinical concept trial to investigate the efficacy and safety of spesolimab compared to placebo in patients with moderate to severe hidradenitis suppurativa (HS).

The primary objective is to estimate the effect of spesolimab compared to placebo for the mean percent change from baseline in total abscess and inflammatory nodule count at Week 12. Secondary objectives are the evaluation of efficacy of spesolimab on secondary endpoints versus placebo.

The comparisons of interest for each efficacy objective are those of all treated patients but excluding the effects of rescue therapy.

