7.2.2 Primary endpoint analyses

The difference in percent change from baseline in total abscess and inflammatory nodule at Week 12 between spesolimab and placebo is the primary endpoint of this trial. All on-treatment data are planned to be included into analysis but any data after use of any rescue therapy will be censored in line with the primary objective to estimate the treatment effect in treated patients assuming they do not receive rescue therapy (primary estimand). To account for the repeated nature of the data, the primary analysis is a restricted maximum likelihood (REML) based approach using a mixed model with repeated measurements (MMRM) comparing the adjusted relevant difference between the two arms.

The analysis will include the fixed categorical effects of treatment at each visit, stratum and the fixed continuous effect of baseline at each visit. Visit will be treated as the repeated measure with an unstructured covariance structure to model the within-patient measurements.

The statistical model will be as follows:

$$y_{ijkm} = \beta_j S_i + \tau_{jk} + \Phi_m + e_{ij}$$

With

- y_{ijkm} response variable for patient i in stratum m at visit j receiving treatment k
- S_i baseline measurement of patient i , $i=1,2,\dots$
- β_j coefficient of baseline effect at visit j
- τ_{jk} effect of treatment k at visit j , $j=3,\dots,9$ and $k=1, 2$
- Φ_m effect of stratum m , $m=1,2$
- e_{ij} random error associated with visit j of patient i .

Errors are independent between patients with $e_{ij} \sim N_z(0, \Sigma)$ and Σ is an unstructured covariance matrix.

The Kenward-Roger approximation will be used to estimate denominator degrees of freedom and adjust standard errors. Due to the exploratory character of this trial no significance test will be done. However, least-squares means (adjusted means) of each arm as well as adjusted treatment differences will be provided together with two-sided 95 %-confidence intervals for each time point.

The patients will be analysed according to the stratum to which they belong (regardless of any mis-assignment to treatment based on identification of the wrong stratum), as such an error occurs before randomization and is therefore consistent with regulatory guidance. Procedures to follow if the analysis fails to converge will be described in the TSAP.

Secondary analysis of the primary endpoint will include:

[figure not shown]

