D1.01#	Washout of previous medication too short LABEL: Washout too short.	Washout period too short – See Table 4.2.2.1:1 in CTP	PPS
D2	Prohibited medication use		

Proprietary confidential information © 2021 Boehringer Ingelheim International GmbH or one or more of its affiliated companies

D2.01#	Use of restricted medication (other than systemic antibiotics) for HS (with potential influence of efficacy data) prior to or up to week 12 Label: Use of restricted medication other than systemic antibiotics for HS	See the list of restricted medication in section 4.2.2 of CTP, manual assessment at MQRM/RPM/DBLM	PPS
D2.02#	Use of antibiotic before week 4 for HS LABEL: Use of antibiotic before week 4 for HS	See section 3.3.4.1 of CTP for details, manual assessment at MQRM/RPM/DBLM	PPS
D2.03#	Inappropriate use of Systemic antibiotics for HS disease worsening at/after week4. LABEL: Inappropriate use of Systemic antibiotics for HS disease worsening at/after week4	Including usage 1) without meeting criteria for HS disease worsening, or 2) longer duration than allowed See section 4.2.2 of CTP for details, manual assessment at MQRM/RPM/DBLM	PPS
E	Missing data	<not specified>	
F	Study specific analysis	<not specified>	
G	Other safety related violations		
G1.01	Pregnancy test not done for woman of child bearing potential before IMP administration LABEL: Pregnancy test not done.	Pregnancy test not done at any visit when it is scheduled and the patient did not yet complete follow-up.	None

PV will be detected manually

Source: BI reference document 'Identify and Manage Important Protocol Deviations (iPD)' [001-MCS-50-413] ([8.12](#)).

¹ See Section 6.3 for population definitions

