Table 6.3: 1 Overview of use of patient analysis sets by class of endpoint and handling of estimand and missing data

Class of Endpoints	ES	RS	SAF	PKS	PPS
Disposition	OR	OR			
Compliance and exposure			OR		
iPD		OR			
Demographic/baseline characteristics		OR	OR		
Concomitant medication		OR			
Primary endpoint			EC-H-MMRM EC-H-MMRM ¹ EC-H-MMRM ⁴ EC-S-MMRM ¹ OC ² , OC-IR ²		EC-H-MMRM ¹
Secondary binary efficacy endpoints			EC-H-NRI, EC-H-NRI ¹ EC-H-NRI ⁴ OC ² EC-H-MI ³		
Secondary continuous efficacy endpoints			EC-H-MMRM EC-H-MMRM ¹ EC-H-MMRM ⁴ EC-S-MMRM ³ OC ²		
Further efficacy endpoints			Binary: EC-H-NRI Continuous: EC-H-MMRM ¹ All: OC ² ,		
Concentration & ADA			OR	OR	
Safety data			OR OC-IR		

¹ sensitivity/further analysis

² descriptive display only

³ selected endpoints.

⁴ subgroup analysis

For explanation of the different approaches with regard to missing data see [Section 6.6](#).

[figure not shown]
EC-H: Hybrid strategy by implementing estimand concept. Any data post rescue medication use will be censored.

EC-S: Supplementary strategy by implementing estimand concept. Any data collected after use of any rescue therapy or restricted medication are censored.

OC = observed cases excluding values after any use of rescue medication.

OC-IR = observed cases including also values after any use of rescue medication.

OR = original results.

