7.4.2 Sensitivity analysis, subgroup analysis, exploratory analysis of the primary endpoint(s)

Sensitivity analysis

As one sensitivity analysis for the primary endpoint, the observed data will be augmented with historical data. The 1368.52 placebo group will be combined with prior historical data for the placebo group from Humira Pioneer I and Pioneer II trials to derive the respective posterior distribution of the primary endpoint. A comparable population according to inclusion criteria in the current trial is obtained by trimming the historical data to patients with baseline total AN count no less than 5 and baseline total draining fistula count no larger than 20. A meta-analytic predictive (MAP) prior will be derived from the trimmed data. Similarly, the observed data of spesolimab group will be combined with a non-informative prior to derive the respective posterior distribution for spesolimab treatment. These posterior distributions will be used to evaluate the posterior treatment difference in primary endpoint between spesolimab and placebo. The posterior median and 95% credible intervals will be reported.

Furthermore, as the historical placebo data is from TNFi-naïve population, an additional sensitivity analysis will only consider the combination of the historical data with the observed data from TNFi-naïve patients in the placebo arm of the current study to derive the respective posterior distribution. The observed data from TNFi-failure patients in the placebo arm of the current study will be combined with a non-informative prior to derive the corresponding posterior distribution. The information from the strata will be weighted per sample size to obtain an overall estimate.

The MAP prior derivations for placebo arm obtained from Humira Pioneer I and Pioneer II trials, as well as posterior distribution for the treatment difference will be implemented following [Section 10.3.1](#).

In addition, the following sensitivity analysis for MMRM may be done:

- Sensitivity analyses utilizing MMRM model on different patients sets (such as the PPS)

Supplementary analysis

Proprietary confidential information © 2021 Boehringer Ingelheim International GmbH or one or more of its affiliated companies
The analysis based on supplementary strategy (EC-S) of handling intercurrent event defined in [Section 5.4.5](#) may be done if the interested event occurs. Any data collected after the intercurrent event will be censored for the timepoint afterwards.

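### Should lesion counts after a permitted drainage or steroid injection get their own analysis of the primary endpoint?

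*Protocol*

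**What the plan says.** Protocol 4.2.2.5 permits two procedures on an acutely painful lesion ("Only two types of interventions are allowed: Intra-lesional steroid and Incision and Drainage (I&D"), up to two in total. It attaches no analysis rule to them.

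The target is set in Protocol 2.1.1: "The comparisons of interest for each efficacy objective are those of all treated patients but excluding the effects of rescue therapy". Protocol 7.2.2 follows it: "All on-treatment data are planned to be included into analysis but any data after use of any rescue therapy will be censored". Rescue, in Protocol 4.2.2.2, "is generally defined as the treatment for disease worsening and includes systemic antibiotics and/or immunosuppressive biologics such as TNF-inhibitors". Neither that text nor the restricted-medication table in Protocol 4.2.2.1 names drainage or intralesional steroid.

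The legend to SAP Table 6.3:1 describes the primary strategy, EC-H, as "Any data post rescue medication use will be censored" and the supplementary strategy, EC-S, as "Any data collected after use of any rescue therapy or restricted medication are censored". SAP 7.4.2 says EC-S "may be done if the interested event occurs". The nearest per-protocol exclusion, deviation D2.01 in SAP Table 6.2:1, carries the comment "See the list of restricted medication in section 4.2.2 of CTP, manual assessment at MQRM/RPM/DBLM".

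SAP 7.4.1 places the definition of the primary intercurrent-event strategy in section 5.4.6, SAP 7.4.2 places EC-S in 5.4.5, SAP 5.1 places the derivation of the count in 10.1.1, and SAP 7.2 places rescue reporting in 7.6.3. None of these four sections is in the public copy.

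**The concern.** The primary endpoint is a count of abscesses and inflammatory nodules, and a procedure on one of them can lower that count directly. A drained abscess that is no longer counted scores as improvement or hides worsening, whatever the study drug did. The plan censors after rescue, which needs a large rise in the count and, for antibiotics, Week 4 or later. It says nothing about a procedure that carries neither condition.

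The readout is a point estimate from 30 against 15 patients, so a few treated lesions in one arm might matter. HiSCR uses the same counts. No published analysis shows whether the estimate depends on these procedures. EC-S is optional and keyed to medication, and the two observed-case displays differ only by values after rescue or investigator-prescribed standard of care.

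**Working it through.** **Inputs from the documents.** 30 spesolimab and 15 placebo patients; SD 45 points per arm; expected change -62% against -20%, a difference of 42; threshold 30 (Protocol 7.5). Minimum baseline count 5 (Protocol 3.3.2). At most two interventions (Protocol 4.2.2.5).

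**Inputs that must be assumed.** The share of patients treated in each arm (pP, pS), lesions per treated patient (L), the share of treated lesions absent only because of the procedure (fP, fS), and the baseline count of treated patients (B).

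**Step 1: the plan's own figure.** SE = 45 × √(1/30 + 1/15) = 14.23. P(difference ≥ 30) = Φ((42 − 30)/14.23) = 0.800, against 80.1% in Table 7.5:1. It reproduces.

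**Step 2: one patient.** Each lesion removed from the count shifts percent change by 100/B: 20 points at B = 5, 10 at B = 10, 6.7 at B = 15.

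**Step 3: between arms.** Shift in the estimated benefit = −(pP·fP − pS·fS) × L × 100/B, and the probability becomes Φ((12 + shift)/14.23).

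| Placebo use | Spesolimab use | L | f (both arms) | B | Shift | P(≥ 30) |
|---|---|---|---|---|---|---|
| 20% | 10% | 1 | 75% | 10 | −0.75 | 78.5% |
| 20% | 10% | 2 | 75% | 10 | −1.5 | 77.0% |
| 10% | 20% | 1 | 75% | 10 | +0.75 | 81.5% |
| 10% | 20% | 2 | 75% | 10 | +1.5 | 82.9% |
| 30% | 10% | 2 | 100% | 10 | −4 | 71.3% |
| 10% | 30% | 2 | 100% | 10 | +4 | 87.0% |
| 30% | 10% | 2 | 100% | 5 | −8 | 61.1% |
| 10% | 30% | 2 | 100% | 5 | +8 | 92.0% |

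The middle cases are 0.75/14.23 = 0.05 to 1.5/14.23 = 0.11 of a standard error. The planned 95% half-width is 1.96 × 14.23 = 27.9 points. The last two rows need every treated patient to sit at the entry minimum.

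The shift is zero whenever the product of use, lesions per user, share absent and 1/B is equal in the two arms. For example, 20% use with 50% absent balances 10% use with 100% absent.

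**Step 4: what a censoring run could show.** Take 3 patients censored per arm (20% of 15, 10% of 30). With seven visits and within-patient correlation of 0.5 to 0.7, the SE is 14.74 to 15.61; the upper value is also the case with no borrowing across visits, 45 × √(1/27 + 1/12). If the procedures had no effect at all, the two estimates would still differ by chance with SD √(14.74² − 14.23²) = 3.8 to √(15.61² − 14.23²) = 6.4 points. The effect sought in the middle case is 0.75 to 1.5 points.

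**Step 5: its cost in precision.** At 20%/10% use the SE rises by 4% to 10%. Without borrowing, 30%/10% use gives 45 × √(1/27 + 1/10.5) = 16.4 (+15%), and 30%/30% gives 45 × √(1/21 + 1/10.5) = 17.0 (+20%).

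**Step 6: what is already recorded.** The Protocol flowchart collects concomitant therapy at every visit, and its footnotes have the diary capture other interventions to manage pain. Protocol 8.3.1 lists start dates of concomitant therapy for the CRF. SAP 7.2 summarises on-treatment medications and non-drug therapies other than rescue, and SAP 7 lists all individual values. Use of these procedures should therefore be visible without a new table, provided that sites enter them as concomitant therapy.

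**The case for a change.** The best case for acting is that a pre-specified check beats a post-hoc argument, and that silence looks like oversight because Protocol 4.2.1 does state the analysis consequence of another permitted steroid use. One patient changing HiSCR status moves the placebo rate by 1/15 = 6.7 points and the spesolimab rate by 1/30 = 3.3.

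A simulation also favours censoring on average. Interventions were triggered by high counts in about 30% of placebo and 15% of spesolimab patients, with per-patient shifts of 10, 20 and 40 points. Retained data gave differences of 39.6, 38.1 and 35.1 against about 41.2 without interventions; censoring gave about 41.

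Some of this stands. The published text does leave open whether D2.01 could catch a permitted intralesional steroid, since it points to all of Protocol 4.2.2. Protocol 4.2.2.5 itself asks only that associated medications reach the medical records. A sentence on either point would do no harm.

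The rest does not carry a change. The simulated recovery holds because censoring there depended only on observed counts; in practice patients are selected for an acutely painful lesion, and missing at random is less secure. The same simulation raised the estimator's SD from about 14.2 to between 16.6 and 17.1. In a single trial, a movement of several points would most likely be chance and could mislead. Censoring would also estimate an effect without procedures, which Protocol 2.1.1 does not ask for.

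**Conclusion.** No change is needed. On the published text, counts after a permitted drainage or injection stay in the primary MMRM, and that is consistent with an objective that removes the effects of rescue only. Whether the four unpublished SAP sections already deal with treated lesions cannot be determined, and text withheld from the public copy cannot be counted as absent from the plan.

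The likely effect is small and its direction unknown: about 0.75 to 1.5 points either way in the middle case, up to 4 at a baseline count of 10 with 30% against 10% use, and 8 only in the extreme case. All of these rest on assumed rates of use and lesion loss, because the documents give none. In an exploratory trial with no testing and a 95% half-width near 28 points, this does not alter how the result is read. A supplementary run remains open to the analysts as a descriptive extra, but it could not settle the question.
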